--------------------------	--

	
 8. Severe pulmonary hypertension 9. Smoking of any kind (not limited to tobacco) within 3 months prior to screening, as documented in the medical history, or unwilling to avoid smoking throughout the study 10. Lower respiratory tract infection requiring antibiotics within 4 weeks prior to screening and/or during the screening period 11. History of malignancy within the past 5 years or ongoing malignancy other than basal cell carcinoma, resected noninvasive cutaneous squamous cell carcinoma, or treated cervical carcinoma in situ 12. End-stage liver disease 13. Renal impairment or end-stage kidney disease requiring dialysis 14. History of unstable or deteriorating cardiac or pulmonary disease (other than IPF) within the 6 months prior to screening, including but not limited to the following: 
 a. Unstable angina pectoris or myocardial infarction b. Congestive heart failure requiring hospitalization c. Uncontrolled clinically significant arrhythmias (e.g., resulted in health care utilization or hospitalization) 15. Any clinically relevant electrocardiogram (ECG) abnormalities, including but not limited to, QT interval corrected for heart rate using Fridericia's formula (QTcF) > 450 msec for males or > 460 msec for females at the Screening Visit (including Day -1) or prior to administration of the initial dose of study drug 16. Any medical condition that, in the opinion of the Investigator, may make the candidate not suitable for the study 17. History of anaphylaxis to intravenous (IV) drugs 18. Any of the following liver function test criteria above specified limits: total bilirubin $> 1.5 \times$ the upper limit of normal (ULN); aspartate aminotransferase (AST) or alanine aminotransferase (ALT) $> 3 \times$ ULN; alkaline phosphatase $> 2.5 \times$ ULN. Note: participants currently receiving nintedanib or pirfenidone as IPF SoC treatment, who have previously presented any liver function test elevations associated with nintedanib or pirfenidone treatment greater than that described above or resulting in dose reduction, treatment interruption, or discontinuation are not eligible. 19. Any of the following at screening: hemoglobin < 10.0 g/dL, neutrophils < 1500 /mm³, or platelets $< 100,000$ /mL 20. Electrical implants such as cardiac pacemaker or perfusion pump 21. Ferromagnetic implants such as aneurysm clips, surgical clips, prostheses, artificial hearts, valves with steel parts, metal fragments, shrapnel, metallic tattoos anywhere on the body, tattoos near the eye, or steel implants, ferromagnetic objects such as jewelry or metal clips in clothing 22. Claustrophobic reactions 23. Research-related radiation exposure exceeds current Radiology Department guidelines (i.e. 50 mSv in the prior 12 months) 24. Unable to lie comfortably on a bed inside the PET/MRI 25. Body mass index (BMI) > 33 kg/m² (limit of the PET/MRI table) 26. Prior or current radiation to the thorax 27. Pregnant or lactating female participants 28. Male participants with pregnant female partners 29. A medical or surgical condition known to affect drug absorption (e.g., major

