4.3 Exclusion Criteria

Participants who meet any of the following criteria will be excluded from the study.

1. Hypersensitivity to PLN-74809 or to any of the excipients to PLN-74809
2. Not a suitable candidate or unlikely to comply with study requirements, in the opinion of the Investigator
3. Receiving any nonapproved agent intended for treatment of fibrosis in IPF
4. Forced expiratory volume during the first seconds of the forced breath (FEV1)/FVC ratio < 0.7 at screening
5. Clinical evidence of active infection, including but not limited to bronchitis, pneumonia or sinusitis that can affect FVC measurement during screening or at randomization
6. Any other condition that prevents the correct assessment of spirometry performance (e.g., a broken rib or chest pain of other origin that prevents adequate forced breathing)
7. Known acute IPF exacerbation or suspicion by the Investigator of such, within 6 months of screening
8. Severe pulmonary hypertension
9. Smoking of any kind (not limited to tobacco) within 3 months prior to screening, as documented in the medical history, or unwilling to avoid smoking throughout the study
10. Lower respiratory tract infection requiring antibiotics within 4 weeks prior to screening and/or during the screening period
11. History of malignancy within the past 5 years or ongoing malignancy other than basal cell carcinoma, resected noninvasive cutaneous squamous cell carcinoma, or treated cervical carcinoma in situ
12. End-stage liver disease
13. Renal impairment or end-stage kidney disease requiring dialysis
14. History of unstable or deteriorating cardiac or pulmonary disease (other than IPF) within the 6 months prior to screening, including but not limited to the following:
 - a. Unstable angina pectoris or myocardial infarction
 - b. Congestive heart failure requiring hospitalization
 - c. Uncontrolled clinically significant arrhythmias (e.g., resulted in health care utilization or hospitalization)

15. Any clinically relevant ECG abnormalities, including but not limited to, QT interval corrected for heart rate using Fridericia's formula (QTcF) > 450 msec for males or > 460 msec for females at the Screening Visit (including Day -1) or prior to administration of the initial dose of study drug
16. Any medical condition that, in the opinion of the Investigator, may make the candidate not suitable for the study
17. History of anaphylaxis to intravenous (IV) drugs

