18. Any of the following liver function test criteria above specified limits: total bilirubin $> 1.5 \times$ the upper limit of normal (ULN); aspartate aminotransferase (AST) or alanine aminotransferase (ALT) $> 3 \times$ ULN; alkaline phosphatase $> 2.5 \times$ ULN.

Note: participants currently receiving nintedanib or pirfenidone as IPF SoC treatment, who have previously presented any liver function test elevations associated with nintedanib or pirfenidone treatment greater than that described above or resulting in dose reduction, treatment interruption, or discontinuation are not eligible.
19. Any of the following at screening: hemoglobin < 10.0 g/dL, neutrophils < 1500 /mm³, or platelets $< 100,000$ /mL
20. Electrical implants such as cardiac pacemaker or perfusion pump
21. Ferromagnetic implants such as aneurysm clips, surgical clips, prostheses, artificial hearts, valves with steel parts, metal fragments, shrapnel, metallic tattoos anywhere on the body, tattoos near the eye, or steel implants, ferromagnetic objects such as jewelry or metal clips in clothing
22. Claustrophobic reactions
23. Research-related radiation exposure exceeds current Radiology Department guidelines (i.e. 50 mSv in the prior 12 months)
24. Unable to lie comfortably on a bed inside the PET/MRI
25. Body mass index (BMI) > 33 kg/m² (limit of the PET/MRI table)
26. Prior or current radiation to the thorax
27. Pregnant or lactating female participants
28. Male participants with pregnant female partners
29. A medical or surgical condition known to affect drug absorption (e.g., major gastric surgery)
30. Participation in a clinical study with an investigational agent in the 30 days prior to screening or 5 half-lives of the investigational drug, whichever is longer trial, apart from PLN-74809
31. Currently receiving and expected to remain on treatment during the study with: potent and concomitant inhibitors or inducers of cytochrome P450 (CYP) 3A4, 2C9 or 2C19; potent inhibitors or inducers of P-glycoprotein (P-gp), breast cancer resistance protein (BCRP) or organic anion transporting polypeptide (OATP) 1B1/1B3 transporters; digoxin (a P-gp substrate with a narrow therapeutic window)

32. Daily use of phosphodiesterase-5 (PDE-5) inhibitor drugs (e.g., sildenafil, tadalafil, other) (Note: Intermittent use for erectile dysfunction is allowed.)
33. Surgical procedures planned to occur during the study period
34. Uncontrolled systemic arterial hypertension

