
Hematology
 
 - Hematocrit (Hct) - Hemoglobin (Hgb) - Mean corpuscular hemoglobin (MCH) - Mean corpuscular hemoglobin concentration (MCHC) - Mean corpuscular volume (MCV) - Platelet count - Red blood cell (RBC) count - White blood cell (WBC) count with differential 
Coagulation
 
 - International normalized ratio (INR) 
Urinalysis
 
 - Appearance - Bilirubin - Color - Glucose - Ketones - Microscopic examination of sediment - Nitrite - Occult blood - pH - Protein - Specific gravity - Urobilinogen 
Other
 
Serum and urine human chorionic gonadotropin (hCG) (females)
	
Serum Chemistry
 
 - Alanine aminotransferase (ALT) - Albumin (ALB) - Alkaline phosphatase (ALP) - Alpha-1-acid-glycoprotein (AAG) - Amylase (reflex lipase if amylase $\geq 1.5 \times$ ULN) - Aspartate aminotransferase (AST) - Bilirubin (total and direct) - Blood urea nitrogen (BUN) - Calcium (Ca) - Chloride (Cl) - Creatinine - Creatine kinase (CK) - Gamma-glutamyl transferase (GGT) - Glucose - High-sensitivity C-reactive protein (hsCRP) - Lactate dehydrogenase (LDH) - Phosphorus - Potassium (K) - Sodium (Na) - Total cholesterol - Total protein - Triglycerides - Troponins - Uric acid
---	---

7.7.2 *Sample Collection, Storage, and Shipping*

Refer to the study manual for details regarding sample collection, storage, and shipping.

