12 PLANNED STATISTICAL METHODS

12.1 General Considerations

This is an exploratory study, with exploratory efficacy and biomarker assessments; as such, no statistical hypotheses are being tested. In general, data will be summarized using statistical summary methods; graphic presentations of data may also be prepared. A statistical analysis plan (SAP), prepared and agreed before final database lock, will describe the analytic approach and methods in more detail.

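### Exclusion 19 gives the platelet limit per mL beside a neutrophil limit per mm³, so as written it is 100 per mm³ and has almost no practical effect

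*Protocol*

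**What the plan says.** Section 4.3 opens its list with "Participants who meet any of the following criteria will be excluded from the study", so meeting any single item excludes a candidate. Item 19 applies at screening and covers three blood measures. It begins "hemoglobin < 10.0 g/dL, neutrophils < 1500 /mm³, or platelets" and ends with the platelet limit, "or platelets $< 100,000$ /mL".

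The synopsis repeats the item with the same pair of units: "neutrophils < 1500 /mm³, or platelets $< 100,000$ /mL".

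Table 1 in Section 7.7.1 lists "Platelet count" under hematology and gives no reporting unit. No other part of the protocol states a platelet limit. The SAP does not restate the eligibility criteria, and its laboratory section (5.12.3) gives no platelet threshold or unit.

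**The concern.** Two cell counts in one sentence are expressed per volumes that differ by a factor of 1000. The neutrophil limit is in a unit that gives it a working range. The platelet limit carries a number that would also work in that unit, but it is attached to a volume 1000 times larger. The synopsis and Section 4.3 agree with each other, so neither can be used to correct the other.

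At stake is whether a numerical safety criterion that the sponsor chose to state does anything. Sections 9 and 10 give threshold-based rules for liver tests and QTc; there is no comparable rule for platelets after entry. The written criterion is also what adherence is judged against (Section 14.5). A site that excluded a candidate at 60,000 per mm³ under item 19 would be departing from the literal text, and a monitor could query the decision. With about 12 participants planned, one disputed eligibility decision concerns about 1/12, or 8%, of the trial.

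**Working it through.** The threshold is a stated criterion, so there is no derivation in the plan to reproduce. The check is a unit conversion.

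**Inputs**
- Platelet limit: 100,000 per mL (exclusion 19, Section 4.3 and synopsis).
- Neutrophil limit: 1500 per mm³ (same sentence).
- Conversion: 1 mL = 1 cm³ = (10 mm)³ = 1000 mm³.

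**Platelet limit in the neutrophil unit**
- 100,000 per mL ÷ 1000 = 100 per mm³.
- Per litre: 100,000 × 1000 = 1.0 × 10⁸.

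**The same number read per mm³** (an assumption, for comparison only)
- 100,000 per mm³ × 1000 = 100,000,000 per mL.
- Per litre: 100,000 × 10⁶ = 1.0 × 10¹¹.
- Ratio to the written limit: 1.0 × 10¹¹ ÷ 1.0 × 10⁸ = 1000.

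**The two limits on one scale**
- Neutrophils: 1500 per mm³ × 1000 = 1,500,000 per mL.
- Neutrophil limit ÷ platelet limit: 1,500,000 ÷ 100,000 = 15. As written, the platelet limit is 15 times lower than the neutrophil limit.

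**Illustrative counts under each reading**

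| Platelets per mm³ | Platelets per mL | Excluded as written (< 100,000 per mL) | Excluded if read per mm³ (< 100,000) |
|---|---|---|---|
| 5,000 | 5,000,000 | No | Yes |
| 10,000 | 10,000,000 | No | Yes |
| 50,000 | 50,000,000 | No | Yes |
| 100,000 | 100,000,000 | No | No |
| 150,000 | 150,000,000 | No | No |

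The counts are chosen for illustration and do not come from the documents. At 10,000 per mm³ the participant is 10,000,000 ÷ 100,000 = 100 times above the written limit. The two readings give the same answer only for counts below 100 per mm³ or at or above 100,000 per mm³; every count between those values is classified differently.

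**The case against.** **The character may have been misread.** The difference between mL and µL is one micro sign, and the text was read from PDF by a program. The two occurrences are not independent evidence, because the same sentence could carry the same fault twice. A micro sign did survive in Section 6.6.2, where an inhibitory concentration is given in µM, but that does not prove that one was not lost here. This objection stands as a condition: the source PDF has to be checked before the unit is treated as the sponsor's.

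**Entry is not unguarded.** A reader might infer that the criterion excludes no one and that participants with very low platelets would be enrolled. The documents do not support going that far. Counts below 100 per mm³ are still excluded. Exclusions 2 and 16 let the investigator turn away an unsuitable candidate, hematology is drawn at screening, and Section 7.7.1 has the investigator review all laboratory results. For a very low count to pass, a physician would have to see it and decide not to act. After entry, hematology is repeated on Day 1 and at Weeks 2, 4, 8, 12 and 14 (Appendix 1), and Section 11 allows withdrawal or stopping of study drug for a clinically significant laboratory change. That last provision concerns change, so by itself it would not pick up a count that was low at baseline and stayed there.

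**No automated failure is shown.** A reader might also picture a programmed eligibility check passing everyone. The protocol describes the IRT for treatment assignment and access to unblinding (Sections 6.4 and 6.5) and the EDC for recording laboratory results (Section 7.7.1). It describes no automated eligibility check. Nor do the documents link pirfenidone or nintedanib to platelet counts, so background therapy adds nothing to this point.

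**Sites may see the slip.** This is a single-center study, and a limit of 100 per mm³ is implausible enough that staff may well read it in the neutrophil unit. That lowers the practical risk, but the criterion then works only because staff depart from the text.

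**Conclusion.** The point holds: the platelet limit in exclusion 19 is inconsistent with its own sentence and, as supplied, equals 100 per mm³. That is exactly 1000 times lower than the same number in the neutrophil unit. Read literally, the only platelet-specific entry criterion has almost no practical effect, and excluding low counts is left to investigator judgment.

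Two assumptions matter. The first is that the unit in the source PDF really is mL. The second is that per mm³ is the right comparison; the neighbouring neutrophil limit suggests this, but the documents never state the intended platelet unit, so the intended threshold cannot be settled from them.

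The severity is minor to moderate. This is an operative safety criterion rather than background text, so it deserves correction, but the slip is recognisable and judgment-based safeguards exist. The sample size statement in Section 12.2 uses no platelet figure, and the SAP analyses do not depend on the criterion.

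**What to change.** 1. Check the source PDF of the protocol for a micro sign in exclusion 19, in both the synopsis and Section 4.3. If both places show one, the point falls away.
2. If the unit is mL as read, the sponsor should confirm the intended platelet threshold and its unit, and then reconcile the two places together in the next amendment. Which threshold is right is for the sponsor to say.
3. Check any eligibility worksheet, or other screening tool if one exists, that was built from the item.

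The cost is one unit in two places plus a short document check. If the site already reads the limit in the neutrophil unit and the sponsor confirms that reading, recruitment does not change. No re-calculation of sample size and no SAP change is needed.

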PLN-74809 showed a favorable safety and tolerability profile after up to 7 days of treatment, with no new safety concerns observed during this dose-escalation study. There were no clinically significant alterations in vital signs, electrocardiogram (ECG) or laboratory parameters across either the SAD or MAD cohorts indicative of a safety signal. There were no deaths reported during or after the study period.

Please refer to the Investigator's Brochure for additional detailed information on this study. (Note that analysis of data from single doses greater than 320 mg and multiple doses greater than 160 mg is ongoing.)

1.1.3 *Ongoing Phase 2 studies*

Four Phase 2 studies evaluating doses of PLN-74809 are ongoing.

Study PLN-74809-IPF-201 is a Phase 2a open-label study to evaluate the effect of PLN-74809 on $\alpha_v\beta_6$ receptor occupancy using positron emission tomography (PET) imaging in participants with IPF evaluating single doses ranging from 60 to 320 mg. Evaluation of target engagement and the safety and tolerability of PLN-74809 is currently ongoing and no new safety concerns have been identified.

Study PLN-74809-IPF-202 is a Phase 2a, multicenter, 3-part, randomized, double-blind, dose-ranging, placebo-controlled evaluation of the safety, tolerability and pharmacokinetics (PK) of once daily treatment with PLN-74809 for 12 weeks in participants with IPF.

Study PLN-74809-PSC-203 is a Phase 2a, multicenter, 2-part, randomized, double-blind, dose-ranging, placebo-controlled evaluation of the safety, tolerability and PK of once daily treatment with PLN-74809 for 12 weeks in participants with PSC and suspected liver fibrosis.

Study PLN-74809-ARDS-204 is a Phase 2a, multicenter, 3-part, randomized, double-blind, dose-ranging, placebo-controlled evaluation of the safety, tolerability and PK of once daily treatment with PLN-74809 for 7-14 days in participants with ARDS associated with at least severe COVID-19.

At the time of protocol finalization, safety and tolerability data from these ongoing Phase 2 studies suggest no new safety concerns.

Please refer to the Investigator's Brochure for additional detailed information on these studies.

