3 INVESTIGATIONAL PLAN

3.1 Overall Study Design and Plan

This is a Phase 2a, single-center, randomized, double-blinded, placebo-controlled study to evaluate type 1 collagen deposition in the lungs following once-daily (QD) treatment with 160 mg PLN-74809 for 12 weeks in participants with IPF.

The study consists of an up to 28-day screening period, a 12-week treatment period, and a 2-week (± 3 days) post treatment follow-up period.

Potential participants who provide written informed consent will be screened for study eligibility up to 28 days before administration of the first dose of study drug. Approximately 12 eligible participants will be randomized in a 2:1 ratio (160 mg PLN-74809 vs placebo; 8 receiving PLN-74809 and 4 receiving placebo) on Day 1 (Visit 3). Study treatment will be administered once daily for 12 weeks. Randomization will be stratified by use of standard of care (SoC) IPF therapy with pirfenidone or nintedanib (SoC use; yes or no).

^{68}Ga -CBP8 PET/MRI scans will be conducted within 7 days prior to baseline and at or within 7 days prior to Week 12, as indicated in the Schedule of Events ([Appendix 1](#)).

Participants who discontinue study drug for safety reasons prior to completion of 12 weeks of treatment will be encouraged to remain in the study to complete all remaining assessments; if this is not feasible, they will be asked to return to the clinic for an Early Termination (ET) visit for follow-up evaluations. If a participant elects to withdraw from the study after the 6th week of randomization, an end of participation ^{68}Ga -CBP8 PET/MRI will be offered to the participant to enhance appropriate data capture.

Potential acute exacerbations, respiratory-related hospitalizations, and/or respiratory-related deaths will be reviewed by an adjudication committee.

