5 STUDY DRUG AND ACCOUNTABILITY

5.1 Description of Study Drug

5.1.1 *Study Drug*

The zwitterion PLN-74809-000, and the phosphate salt PLN-74809-020 are derivatives of the parent form PLN-74809. Both are formulated as immediate-release tablets. In this study, the phosphate form will be tested, hereafter referred to as PLN-74809.

PLN-74809 drug product is supplied as 80-mg immediate release tablets. The PLN-74809 tablets are manufactured by dry granulation with standard excipients (microcrystalline cellulose, mannitol, crospovidone, magnesium stearate, and butylated hydroxytoluene), tablet compression, and spray coating of tablets.

5.1.2 *Placebo*

A corresponding matching placebo will be provided.

5.1.3 *PET Tracer*

The ^{68}Ga -CBP8 PET/MRI tracer is not considered a study treatment but is an investigational tool used during the PET procedure for obtaining the images necessary for this trial. ^{68}Ga -CBP8 is given as an intravenous injection within 7 days prior to baseline and at or within 7 days prior to Week 12. The radiochemical dose is up to 12.9 mCi but in practice, the dose has averaged 5.5 mCi per subject.

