7.10 Pharmacodynamic Assessments

7.10.1 PET/MRI Imaging for the Assessment of Type 1 Collagen Deposition

All PET/MRI will be performed at the Martinos Center for Biomedical Imaging at Massachusetts General Hospital. PET imaging will be performed at prespecified times according to the Schedule of Events ([Appendix 1](#)) using the collagen-targeted tracer, ⁶⁸Ga-CBP8 as synthesized at the Martinos Center for Biomedical Imaging, and following predefined instructions as detailed in the Radiology Manual for the study. The radiochemical dose is up to 12.9 mCi per administration; but in practice, the dose averages to 5.5 mCi per subject. The total amount of radiation exposure from the PET/MRI is equal to a whole-body exposure up to 22 mSv (11 mSv per administration of ⁶⁸GaCBP8). Blood samples will be obtained prior to each PET/MRI and will be stored for future analyses. Details for blood sample collection and processing are detailed in the Radiology Manual.

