APPENDIX 1 SCHEDULE OF EVENTS

	Screening		Treatment						EoS / ET
	Visit 1	Visit 2	Visit 3	Visit 4	Visit 5	Visit 6	Visit 7 ^a	Visit 8 ^a	
	Day -28 to Day -1	Pre- Baseline Day -7 to Day -1	Baseline Day 1	Week 2 Day 14 (±2 days)	Week 4 Day 28 (±2 days)	Week 8 Day 56 (±3 days)	Day 84 (-7days)	Week 12 Day 84 (±3 days)	Week 14 Day 98 (±3 days)
Informed consent	X								
Medical history	X								
Demographics (age, sex, race)	X								
Serum pregnancy test	X								
Check inclusion and exclusion criteria	X		X						
Complete physical examination (including height and weight)	X								
Targeted physical examination			X	X	X	X		X	X
Randomization			X						
FVC ^{b,c}	X		X		X	X		X	X
FEV1 ^c	X								
DLco	X								
Cough VAS	X		X	X	X	X		X	X
Vital signs (post 3 minutes, supine; approx 2 hours post dose and around the time of the ECG)	X		X	X	X	X		X	X
Tripple 12-lead ECG (post 10 minutes, supine; at least 2 hours post dose and prior to the PK sample) ^{d,e}	X		X	X	X	X		X	X
Hematology (post 8-hour fast)	X		X	X	X	X		X	X
Clinical chemistry (post 8-hour fast) ^f	X		X	X	X	X		X	X
Coagulation (post 8-hour fast)	X		X	X	X	X		X	X
PET/MRI scan		X						X	
Pharmacokinetic sample plasma ^g			X		X			X	X ^{e,f,h}

	Screening	Treatment								EoS / ET
	Visit 1	Visit 2	Visit 3	Visit 4	Visit 5	Visit 6	Visit 7 ^a	Visit 8 ^a	Visit 9	
	Day -28 to Day -1	Pre-Baseline Day -7 to Day -1	Baseline Day 1	Week 2 Day 14 (±2 days)	Week 4 Day 28 (±2 days)	Week 8 Day 56 (±3 days)	Day 84 (-7 days)	Week 12 Day 84 (±3 days)	Week 14 Day 98 (±3 days)	
Pharmacokinetic nintedanib/pirfenidone sample plasma x 2 (predose and at least 2 hours post dose to PLN-74809) ⁱ			X		X			X		X ^{e,f,h}
Pharmacogenomic sample			X							
Plasma biomarker samples			X		X			X		
Serum biomarker samples			X		X			X		
Urine biomarker samples			X		X			X		
Urine pregnancy test (positive tests will be confirmed with a serum test)			X		X	X		X		X
Urinalysis (dipstick, followed up by micro if abnormal)	X		X		X	X				X
Adverse events				↔						
Concomitant medications				↔						
Study drug administration (empty stomach: 2 hours predose and 2 hours postdose) ^j				↔						
Study drug dispensing			X		X	X				
Study drug accountability					X	X		X		X

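### Exclusion 23 limits earlier research radiation to 50 mSv but leaves out the up to 22 mSv this study itself adds: a minor, cheap wording gap

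*Protocol*

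**What the plan says.** Exclusion 23 in Protocol Section 4.3 (repeated in the Synopsis) excludes a candidate when "Research-related radiation exposure exceeds current Radiology Department guidelines (i.e. 50 mSv in the prior 12 months". The study's own dose is given separately in Section 7.10.1: "The total amount of radiation exposure from the PET/MRI is equal to a whole-body exposure up to 22 mSv", at 11 mSv for each tracer administration. Section 3.1 sets the timing: "PET/MRI scans will be conducted within 7 days prior to baseline and at or within 7 days prior to Week 12". On tracer activity, Section 5.1.3 states: "The radiochemical dose is up to 12.9 mCi but in practice, the dose has averaged 5.5 mCi per subject".

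In the Schedule of Events (Appendix 1), the row "Check inclusion and exclusion criteria" is marked at Visit 1 and at Visit 3 (Day 1) only. The first scan is at Visit 2, between those checks. The second comes around Week 12, after both. No text in the protocol connects the 22 mSv with the 50 mSv, and the withdrawal reasons in Section 11 do not mention radiation.

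**The concern.** A limit on recent research radiation protects most when it takes in the dose the candidate is about to receive, and here that dose is known in advance. Other criteria in the same list do look forward: 31 (medication expected to continue), 33 (planned surgery) and 35 (likely transplantation). Exclusion 23 does not.

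Two things can follow if it is applied as written. A participant may finish above 50 mSv of research exposure in 12 months without any check having flagged it. Or a candidate may receive a baseline scan that makes the same candidate ineligible a few days later: a radiation dose with no follow-up scan and so no change from baseline. What is at stake is a small amount of avoidable exposure. The statistical analysis is not affected.

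**Working it through.** **Inputs.** Limit 50 mSv, prior 12 months (Section 4.3, exclusion 23). Dose per scan up to 11 mSv (Section 7.10.1). Two scans (Section 3.1). Checks at Visit 1 and Day 1 (Appendix 1). Tracer activity: maximum 12.9 mCi, average 5.5 mCi (Section 5.1.3).

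**The plan's own figure.** 2 × 11 = 22 mSv, which agrees with Section 7.10.1.

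**Maximum tracer dose, Day 1 check counts the first scan.**
- Highest prior exposure that keeps prior plus both scans within 50: 50 − 22 = 28 mSv.
- Highest prior exposure that passes Day 1: 50 − 11 = 39 mSv.
- Above 28 and up to 39 mSv: passes both checks and ends above 50, up to 39 + 22 = 61 mSv.
- Above 39 and up to 50 mSv: passes Visit 1, is scanned (up to 50 + 11 = 61 mSv), then fails on Day 1.

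**Maximum tracer dose, Day 1 check does not count the first scan.** Any prior exposure up to 50 mSv passes, and the end total can reach 50 + 22 = 72 mSv. The text does not say which reading applies.

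**Average activity.** This assumes that 11 mSv corresponds to 12.9 mCi and that dose scales linearly with activity.
- Per scan: 11 × 5.5/12.9 = 4.69 mSv; two scans, 9.38 mSv.
- Prior exposure that passes both checks and ends above 50: from 50 − 9.38 = 40.62 to 50 − 4.69 = 45.31 mSv.
- Highest end total: 45.31 + 9.38 = 54.69 mSv, or 50 + 9.38 = 59.38 mSv if Day 1 ignores the first scan.

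**How recent the prior exposure must be.** There is no Day 0, so Day d is d − 1 days after Day 1. For exposure to be within 365 days of the Week 12 scan:

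| Week 12 scan on | Prior exposure no more than this many days before Day 1 |
|---|---|
| Day 77 | 365 − 76 = 289 |
| Day 84 | 365 − 83 = 282 |
| Day 87 | 365 − 86 = 279 |

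This is about 9 months.

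**How much prior exposure that is.** 28/11 = 2.5, so more than 2.5 earlier scans at 11 mSv. At average activity, 40.62/4.69 = 8.7, so more than 8.7 earlier scans.

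**The case against.** The strongest reply is that nothing here is an error. The 50 mSv is written as an entry limit on past exposure, the study dose is disclosed openly alongside it, and no text sets a cap on the two together. The criterion also defers to a department guideline, and imaging follows a Radiology Manual. Neither is among the documents, and either may already count planned dose. The investigator can in any case turn away an unsuitable candidate under exclusion 2. With about 12 participants, perhaps none will come near the range.

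Most of this stands and sets the size of the point. It does not remove it. The parenthesis in exclusion 23 defines the limit by prior exposure, and that is the text site staff will apply. If practice already counts the planned dose, rewording only records it.

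Two stronger readings are tempting. A reader might infer that the protocol breaches its own radiation limit. It does not, because 61 and 72 mSv exceed no limit that the documents state for prior plus study dose. A reader might also infer a route for heavily exposed participants from exclusion 30, which exempts earlier PLN-74809 studies from its washout ("5 half-lives of the investigational drug, whichever is longer trial, apart from PLN-74809"), since an ongoing PLN-74809 study measures "receptor occupancy using positron emission tomography (PET) imaging in participants with IPF evaluating single doses ranging from 60 to 320 mg". But exclusion 30 is a drug washout rule, and research scans older than the washout would be allowed without the exemption. Exposure from that study would still count in full under exclusion 23. Its dose is not given, and no text says its participants will enrol here.

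**Conclusion.** The gap in wording is real and minor. Exclusion 23 omits the study's planned exposure. The Day 1 check can take in the first scan, and nothing takes in the second. At maximum tracer dose the affected range of prior exposure is above 28 and up to 39 mSv for ending above 50 (at most 61), and above 39 and up to 50 mSv for a baseline scan followed by exclusion. At average activity the excess over 50 is at most about 5 mSv, or about 9 mSv if Day 1 ignores the first scan.

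This rests on four assumptions: 50 mSv is a sensible benchmark for total research dose over 12 months; the unseen guideline does not already count planned dose; the prior exposure is recent enough; and the end-of-participation scan offered after week 6 replaces the Week 12 scan, so there is no third dose. The documents do not show how many candidates, if any, fall in these ranges, and it is probably rare. The point is a cheap improvement to participant protection and not an error in the plan.

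**What to change.** Keep the existing look-back and add the planned dose, for example: *Research-related radiation in the 12 months before screening, together with the dose planned in this study (up to 22 mSv), is above the Radiology Department's current limit (50 mSv).* Apply it at Visit 1, before the baseline scan. At maximum tracer dose this admits at most 28 mSv of prior exposure. Anchoring to screening also means the first scan is counted once, as planned dose. Change the Synopsis copy to match, and have the institution's radiation-safety body confirm the limit and whether it already counts planned dose.

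Do not swap the look-back for a 12-month window ending at the Week 12 scan. That would drop exposure from about 290 to 365 days before Day 1. Someone with 55 mSv on Day −300 is excluded now. Under such a window that exposure would be 300 + 83 = 383 days before a Day 84 scan and would not count, yet the baseline scan would bring the 12-month total to 55 + 11 = 66 mSv.

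The cost is one phrase in two places and the loss of a few candidates with high prior research exposure. Some of these would never have passed 50 mSv. With 30 mSv on Day −300, for instance, the new test gives 30 + 22 = 52 and excludes, although the 12-month total would be at most 30 + 11 = 41 mSv at baseline and 22 mSv at Week 12.
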